- (3) Patients who should undergo other long-term merger resection during distal gastrectomy. (except cholecystectomy)
- (4) Patients with significant ascites by CT.
- (5) Patients with cirrhosis in CT brfore surgery
- (6) Patients with heart disease (history of uncontrolled hypertension, angina or coronary artery disease, history of cardiac muscle disease, Ejection Fraction <50%)
- (7) Patients with inappropriate renal function (serum creatinine > 1.4 mg/dL or BUN > 26 mg/dL)
- (8) Patients with abnormal coagulation (PT INR > 1.2 or aPTT > 45 sec)
- (9) Uncontrolled diabetic patients
- (10) Inflammatory bowel disease patients including Crohn's disease, ulcerative colitis, tuberculous enteritis
- (11) Patients taking aspirin or platelet inhibitors within 5 days before surgery
- (12) Patients taking anticoagulants

- (13) Patients with the history of steroid use which needs stress dose inoculation
- (14) Pregnancy
- (15) Other patients who are deemed unable to participate in the clinical trial by the tester
- (16) History of sensitivity to iodine, in case the test using indocyanine green is applied
- (17) Previous history of gout

3) Target number of subjects and basis of calculation

Total target number: 189, competitive enrollment at SNUH and SNUBH Calculation methods of the subjects

Primary evaluation variable: Cerum CRP value on Post-op 2nd day **Subjects of the study**

Main analysis group

- A. Ultrasonic shears
- B. Bipolar sealing device

Explorative analysis group

C. Hybride device

Study hypothesis:

- Null hypothesis: No difference in CRP value on post-op 2nd day between two groups.
- Alternative hypothesis: Difference in CRP value on post-op 2nd day between two groups.

Hypothesis for calculation of number of subjects:

- (1) Level of significance, $\alpha = 0.05$
- (2) Ratio between groups, group A: group B = 1:1
- (3) Type 2 error (β) is 0.20, retaining power of the test at 80%
- (4) Ultrasound dissector and Bipolar's post-op's CRP average and standard deviation was 11.5 ± 6.6 and 8.0 ± 2.8 from preceding research of "Research of availability and safety in using Articulating bipolar vessel sealer system in early Robotic gastrectomy in early stage gastric cancer". Subjected patients were 17, small in numbers and it was for Robotic LAP surgery, not conventional LAP surgery. Therefore, to avoid chances for reflecting not enough subjected patients, we have calculated subjected patient numbers from conservative standard deviation.

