A Statistical Analysis Plan (SAP) will be created before the database locks. A blinding review of the data will focus primarily on issues related to the exclusion of patient or patient data from missing and analyzed data.

The subjects to be validated for the data obtained from the subjects of the clinical trial are

classified into the ITT (intention-to-treat) analysis group and the PP (per protocol) analysis target group.

- ITT analysis group consisted of all randomized subjects after satisfying the selection / exclusion criteria.
- The subjects who underwent the PP analysis were those who completed the clinical trials of the ITT target group, and observed the primary efficacy variables as planned without violating the critical clinical trial plan. Completion of the clinical trial is defined as discharge following normal procedure without further hospitalization after surgery. Critical clinical trial protocol violations include:
 - · Violation of selection / exclusion criteria
 - · Random assignment violations
 - Take medication for concomitant medication
 - In case of any other serious clinical trial protocol violation
- The analysis of the basic characteristics of the patients, including demographic data and clinical history data, is evaluated using the ITT analysis group. All of the validation variables were analyzed for the ITT group and the PP group. The results of the study on serum CRP at day 2 postoperatively were used as the main evaluation group.

Safe Safety evaluation variables such as adverse events and adverse reactions are analyzed using the safety analysis target group.

- The safety analysis group consisted of all subjects who underwent randomized placement.
- Statistical tests for all efficacy / safety parameters should be performed at the 5% significance level. If the data do not meet the assumptions needed to perform a parametric test, a non-parametric test such as the Wilcoson rank-sum test is performed.

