A multivariable analysis of primary and primary secondary efficacy variables is performed. Multivariate analysis uses multiple linear regression models or multiple logistic regression models depending on the type of outcome variable. The main independent variable is the test, we will include the gender and stage of the stratified variables used in randomization in the model and the perturbed variables identified in the demographic and clinical history data analyzes to control the effect. For repeated measurement data, perform a multivariate analysis using the generalized estimation equation (GEE). If a significant interaction effect is found between the treatment group and the participating laboratories and / or the treatment group and the confounding variables, the effect is controlled by including the interaction term in the multivariate model.

• The content of the pre-planned subgroup analysis to be performed in this trial is as follows:

- Gender Male Female)
- BMI (<25 / ≥25)
- Cancer stage (TNM stage)
- Operator
- In vitro / Internal Anastomosis
- The differences between the groups were assessed using the Student's t-test (or the corresponding nonparametric Wilcoxon rank-sum test) or the χ2 test (or Fisher's exact test, the corresponding nonparametric method) Analysis. If control of disturbance variables is required, multivariate analysis is performed.

9-2) Treatment of missing values.

In general, the missing value will be treated as a missing state, and no alternative missing statistic is used. Therefore, only observations will be used for data analysis. Discrepancies data are replaced by missing values at the responsibility of the clinical trial manager.

10) Clinical trial and treatment standard

The same type of treatment and treatment will be given to patients with general gastric cancer who are being treated at Seoul National University Hospital.

11) Study Schedule

- 42 months after IRB approval: registration of clinical trial subjects and clinical trials
- 42 months ~ 48 months: Data analysis and presentation

12. Data and Safety Monitoring Plan

1) The person in charge of monitoring

- * Monitoring supervisor: [name], Associate Professor, Surgery, Seoul National University Hospital
- * Person in charge of monitoring: [name], Department of Nurse, Seoul National University Hospital

2) Data and safety information monitoring items

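### The five planned subgroup factors come with between-group tests only; no treatment-by-factor interaction test is tied to them, so the plan does not show how a difference in effect between levels will be judged

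*Combined protocol and SAP*

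**What the plan says.** Section 11, item 9-1) introduces the list with "The content of the pre-planned subgroup analysis to be performed in this trial is as follows". It names gender, BMI (below 25, or 25 and above), TNM stage, operator, and extracorporeal or intracorporeal anastomosis. The closing bullet reads "The differences between the groups were assessed using the Student's t-test" and offers Wilcoxon, chi-square or Fisher as alternatives, with multivariable analysis where confounding has to be controlled. Earlier in the same item: "Statistical tests for all efficacy / safety parameters should be performed at the 5% significance level". No multiplicity rule, interpretation rule or exploratory label is attached to the subgroup results.

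The paragraph just above the list describes multivariable models for the primary and main secondary variables. It names gender and stage as covariates. If treatment interacts significantly with the participating sites or with confounding variables, the interaction term is kept in the model so that its effect is controlled.

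**The concern.** A test inside one level asks whether the devices differ in that level. A subgroup analysis asks whether the device difference changes from one level to another, and two within-level p values do not answer that. Splitting the sample cuts power in each part, so one significant and one non-significant level is a common result even when the effect is the same in everyone.

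The study means to give surgeons a basis for choosing instruments (section 11, item 6). A statement that one device lowers CRP in men but not in women, or with one type of anastomosis only, is the kind of result such readers would act on. It could arise from smaller samples and chance alone.

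**Working it through.** **Inputs (section 10, item 3).** The pilot is given as "average and standard deviation was 11.5 ± 6.6 and 8.0 ± 2.8", a difference of 11.5 − 8.0 = 3.5. The SD is 6.6 in both arms: "we have calculated subjected patient numbers from conservative standard deviation", and the sample size table shows 6.6 twice. Allocation is "group A: group B = 1:1". Alpha is 0.05, taken as two-sided because the alternative is non-directional ("Alternative hypothesis: Difference in CRP value on post-op 2nd day between two groups"). Power is 80%. Subgroup sizes are not given, so the splits below are assumptions.

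**The plan's own figure.** n per arm = 2(1.96 + 0.8416)² × 6.6² / 3.5² = 2 × 7.849 × 43.56 / 12.25 = 55.8, or 56 by the normal approximation. The t-based solution is 56.8, so 57, as stated. Then 57 / 0.9 = 63.3, and 63 × 3 = 189. Both figures reproduce.

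**Power inside one half.** A 50:50 factor leaves 57 / 2 = 28.5 per arm in each level. The standard error is 6.6 × √(2 / 28.5) = 1.748 and the non-centrality is 3.5 / 1.748 = 2.00. The t-test power is p = 0.503.

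**Discordance.** The chance that exactly one of two complementary levels is significant, when the true effect is identical in both, is p₁(1 − p₂) + p₂(1 − p₁). For equal halves this is 2p(1 − p).

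| True uniform difference | Power per half | Exactly one half significant |
|---|---|---|
| 0 | 0.050 | 9.5% |
| 1.0 | 0.087 | 16% |
| 1.75 | 0.166 | 28% |
| 2.5 | 0.290 | 41% |
| 3.5 (planned) | 0.503 | 50% |
| 5.0 | 0.802 | 32% |

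With 63 per arm the planned-effect figure is 49.6%. A simulation of 3,000 trials with 57 per arm gave 48.9%.

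**Unequal splits at the planned effect.** 60:40 gives 51%, 70:30 gives 55%, 80:20 gives 61% and 90:10 gives 69%. For 70:30, for example, the powers are 0.648 and 0.325, and 0.648 × 0.675 + 0.325 × 0.352 = 0.552.

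**Five factors together.** With five independent 50:50 factors, at least one is discordant in about 83% of simulated trials under the planned effect and 29% under no effect.

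**False positives when there is no effect.** Five two-level factors give 10 tests; more levels for stage or operator raise the count. Treating the tests as independent gives 1 − 0.95¹⁰ = 40%, 1 − 0.95¹¹ = 43% and 1 − 0.95¹³ = 49%. These are too high, because every factor re-cuts the same patients. Simulation with the overlap kept (57 per arm, equal splits) gives about 29% for 10 tests, 33% for 11 and up to 41% for 13.

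**With an interaction test.** The false-difference rate is 5% per factor whatever the overall effect (simulated 4.4% to 5.2%). For power against an interaction of 3.5 at a 50:50 split, the standard error is 6.6 × √(4 / 28.5) = 2.473 and the non-centrality is 3.5 / 2.473 = 1.42, so power is about 29%. Five independent unadjusted tests carry 1 − 0.95⁵ = 22.6%.

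**The case against.** The strongest reply is that the plan does look at interaction. Keeping a significant interaction term presupposes that it was tested, and gender and stage are named covariates in those models. Anastomosis type is a randomisation factor (section 11, items 1 and 2), and 9-1) means to adjust for randomisation factors, although the ones it names are gender and stage. A reader might therefore infer that interaction is never tested, and that reading is not supported. What stands is narrower. The interaction provision serves adjustment, is not connected to the subgroup list, and does not name BMI, operator or anastomosis type.

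A second reply is that the t-test bullet does not say the tests are run inside each level, nor that contrasting p values will be read as subgroup differences. Both are inferences from the layout, and the bullet could be a general rule for 9-1). This also stands. On that reading, though, the subgroup list has no method of its own, and the same addition is needed.

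A third reply is that no decision rests on subgroups, since the stated main comparison is A against B. That is correct and limits the importance of the point.

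**Conclusion.** The concern holds in limited form, as a desirable improvement that does not touch the primary comparison. The subgroup list has no interaction test tied to it, and the tests that accompany it cannot show that an effect differs between levels.

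A reader might infer that false subgroup contrasts appear half the time whenever the effect is uniform. The documents do not support that in general. The 50% figure applies to day 2 CRP, a two-level factor split equally, and a true difference equal to the full planned 3.5, which came from a pilot of 17 patients having robotic surgery. The documents give no subgroup sizes, no number of operators or stage levels, and no planning figures for the chi-square endpoints, so nothing is claimed for those. The 29% to 41% range for false positives likewise rests on assumed equal splits and level counts.

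**What to change.** In the SAP that 9-1) says will be written before database lock, specify for each of the five factors a model with treatment, factor and treatment-by-factor terms. Report the interaction p value, and show the A minus B difference with its 95% confidence interval in each level. Make no significance claims within levels, and label the results exploratory. For anastomosis, use the type entered at randomisation.

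The cost is some wording and a few extra models; no new patients, data or procedures are needed. The drawback is that most interaction tests will be inconclusive at the power shown above. Five unadjusted tests also still leave about a 23% chance of at least one false signal, which is a further reason for the exploratory label.
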